8.2 Compensation

We will collect behavioral assessments at baseline (BL), 3, 6, 9, and 12 months. Participants will earn up to \$340 for completing the 5 behavioral surveys. Amounts per assessment vary based on estimated survey duration (BL-\$50, 3mo-\$35; 6mo-\$50, 9mo-\$35, 12mo-\$60). Any participant who completes four of the five behavioral assessments will receive a \$50 bonus incentive at the end of the study. We will collect HemaSpot blood samples for HIV Viral Load from HIV-positive participants at BL, 6, and 12 months. For equipoise, we will also offer free in-home HIV testing kits for all HIV-negative and HIV-unknown YBLMT. Participants will receive \$20 for using the prepaid shipping packaging to return HemaSpot device to the lab for processing (if HIV-positive) or for uploading a photograph of the HIV test stick that shows their in-home HIV test result (if HIV-negative or sero-unknown). HIV-positive participants are eligible for the incentive if they return their HemaSpot device to the lab within 45 days of receiving it. If an HIV-positive participant submits a HemaSpot device with a sample that cannot be processed and we confirm in the app's paradata that they have viewed the instructional video, they will be offered a chance to redo the

test kit. If they complete a replacement test and mail it to the lab, they will receive another \$20 incentive, regardless of the specimen's viability.

Participants who report seroconverting during the study or who upload a positive HIV test stick photo, after receiving confirmatory testing will be eligible to begin receiving HemaSpot device testing and incentives following the study's planned schedule. We will use paradata metrics to characterize users' engagement across the three arms.

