4.0 SELECTION AND ENROLLMENT OF STUDY PARTICIPANTS

4.1 Inclusion Criteria (All study arms)

- Aged 15-29 years (inclusive) at time of screening
- Identify as Black/African American and/or Latino/Hispanic
- Current U.S. resident (verified by zip code)
- Speak and read English
- Report anal intercourse in the past 6 months
- Assigned male sex at birth (no restrictions on current gender identity)
- Has a smartphone
- If HIV-positive, does not report a hemophilia diagnosis or current use of anti-coagulation medication

Additional Inclusion Criteria (Referred Peers from Peer-Referral Arm)

- Invited by current participant in Intervention Arm 2 (approximately 300 participants)
- Any race/ethnicity

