4.2 Exclusion Criteria

- Under the age of 15 years
- Over 29 years of age
- Does not speak or read English
- Assigned female at birth
- Reports 0 episodes of anal intercourse in the past 6 months
- Currently incarcerated
- Planning to move out of the United States in next 12 months
- Does not reside in the United States
- Does not have a smartphone
- If HIV-positive and reports a hemophilia diagnosis or current use of anti-coagulation medication

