5.2 Locator/Contact Information

Once a participant has been consented, enrolled, and downloaded the study app, they will be asked to provide a phone number in addition to their email address where they can be reached. Participants will also be asked to provide their mailing address so we can send their HIV test kit or HemaSpot device to them. Study staff will not send mail unless the participant has confirmed their mailing address and is aware they will be receiving a package. The app will assure participants that HIV test kit and HemaSpot packaging does not reveal their participation in a research study. Additionally, the app will tell participants that all email and text message correspondence will not include any protected health information or information related to study participation.

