5.4 Intervention/Investigation Procedures

5.4.1. Randomized Trial Design

We will test whether a smartphone application (app) intervention (HMP Stigma) that promotes user-generated content and engagement to address intersectional stigma is associated with *successful engagement in care* as compared to an information-only control arm consisting of online informational articles and resources curated for YBLMT (Specific Aim 1). We will then examine how user engagement mediates the changes observed in stigma and HIV care outcomes across the 12-month follow-up period (Specific Aim 2). To describe how the social network composition of HMP Stigma affects user engagement and our HIV prevention and care outcomes across a 12-month follow-up period (Specific Aim 3), we will allow the composition of the intervention networks to vary. Participants randomized to Intervention Arm 1 will engage in a researcher-created network where half of the participants are HIV-positive. Participants randomized to Intervention Arm 2 will engage in a peer-referred network in which they may invite 2 peers (irrespective of race/ethnicity and/or HIV status) into the study. All participants who are randomized into Arm 2 will be HIV positive and we assume that peers they refer will be a mix of HIV-negative, HIV-positive, and HIV-unknown status.

5.4.2 HemaSpot Package, Delivery and Tracking: 120

At baseline and months 6 and 12, HIV-positive participants will be mailed a HemaSpot package which contains: 1) one HemaSpot kit with all necessary materials to perform a finger prick, a biohazard bag, and study labels; 2) an instructional booklet for how to properly collect a specimen for the HemaSpot device; 3) a return envelope addressed to the processing lab with pre-paid postage; and 4) a lab sheet which includes the participant's study ID. The U. Penn team will

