5.4.3 HIV Testing

Participants who self-report as HIV negative or unknown will be able to request up to 3 in-home OraQuick HIV tests. These HIV tests help maintain equipoise with the HemaSpot procedures for HIV-positive counterparts in the trial. We have made these HIV test kits optional. Some participants may benefit from an in-home test if they experience HIV stigma in their communities, yet others may prefer to get tested in-person (e.g. at a local community-based agency, primary care doctor, or testing bus). We will ask participants to upload a photo to the app of the HIV test stick that shows their test result. This is also an optional activity. In post hoc analyses, we will compare those who requested in-home test kits with those who report testing at community agency in the follow-up assessments. If participants report a HIV positive result (whether through in-home test kit testing results, a flagged HIV status change in their follow-up surveys, or by notifying the study team directly in the app), our Care Navigator will reach out within 3 business days to support and facilitate linkage to resources and care, including identifying a convenient location for confirmatory testing (if needed) at a local agency. The study team will not report HIV positive OraQuick results to local health departments, as this is a screening test, not a diagnosis. The Care Navigator will encourage and support participants in seeking confirmatory testing and linkage to care for the remainder of their time in the study.

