11.2 Participants' Confidentiality

11.2.1 Risks

The measurements that are involved in this study require finger pricks to collect blood samples. This procedure may cause local discomfort, bleeding, or bruising. This measurement should not be condisered greater than minimal risk in and of itself given its routine use in general health care delivery.

To minimize the risk of participants feeling uncomfortable about answering personal questions, we will use Computer Assisted Self Interview (CASI) methods for the study's surveys. In CASI, participants read and respond to survey questions on a laptop, tablet, smartphone.

To minimize risks to confidentiality, we will secure study data with all appropriate physical, electronic and operational protections. Data will be stored in a physically secure environment. All data files will have encryption and strong password protection. Any identifiable data will either be stored on University of Pennsylvania or UNC-CH's secure servers or will be on fully encrypted laptops. CASI surveys and online eligibility screening will take place on an encrypted commercial survey website, Qualtrics. This site has been used by the investigators for numerous online surveys with MSM with no data security breaches. Access to data will be on a role-based standard; only those study staff who require access to each type of data to complete their study-related roles will be allowed access. All study staff will be trained in security and confidentiality procedures, and will sign a confidentiality agreement before receiving access to any participant data.

We will also develop procedures to minimize indirect disclosure that a participant is participating in an HIV-related research study, or a study that enrolls MSM and transgender women. No study-related messages will ever mention HIV prevention or the nature of the research study. Additionally, all scripts for email, text message, and telephone contact with participants will be reviewed and approved by the University of Pennsylvania's IRB before being used for contact with participants (see "HMP SOP-Communications.docx").

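### The hemophilia/anticoagulant restriction covers only people who are HIV-positive at entry, and section 8.2 does not carry it over to seroconverters who become eligible for the same finger-prick kits

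*Combined protocol and SAP*

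**What the plan says.** The inclusion criterion in section 4.1 reads "If HIV-positive, does not report a hemophilia diagnosis or current use of anti-coagulation medication", and section 4.2 mirrors it as an exclusion: "If HIV-positive and reports a hemophilia diagnosis or current use of anti-coagulation medication". Both are entry criteria and both are conditional on HIV status, which section 3.1 takes from self-report at baseline.

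Section 5.4.2 describes the procedure involved, which is scheduled three times (baseline, month 6 and month 12). The text reads: "HIV-positive participants will be mailed a HemaSpot package which contains: 1) one HemaSpot kit with all necessary materials to perform a finger prick". Participants who are HIV-negative or of unknown status may instead request oral-fluid self-tests (5.4.3).

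Section 8.2 provides for a change of status during the trial. Participants who report seroconverting, or who upload a photograph of a positive test, "after receiving confirmatory testing will be eligible to begin receiving HemaSpot device testing and incentives following the study's planned schedule".

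On the hazard itself, section 11.2.1 says of the finger prick: "This procedure may cause local discomfort, bleeding, or bruising". It then adds: "This measurement should not be condisered greater than minimal risk in and of itself given its routine use in general health care delivery".

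**The concern.** At entry the criteria are coherent. People who will be asked to prick a finger are screened for bleeding risk, and people who will only use an oral swab are not. The protocol does not state this reason, but it is the evident one.

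The coherence is lost when someone moves from the second group to the first. Section 8.2 opens the HemaSpot schedule to seroconverters and does not bring the bleeding restriction with it. The restriction is tied to status at entry, when it should be tied to the procedure.

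What is at stake is participant safety in a very small number of people. Specimens are self-collected from a mailed kit, and section 8.2 pays $20 for each return. No sample size, power figure or analysis depends on the point.

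**Working it through.** No figure in the plan bears on this, so there is nothing to reproduce. The check has two parts: a reading of the relevant sections, and a rough estimate of how many people could be affected.

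**Reading the sections together**

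| Step | Section | What it provides |
|---|---|---|
| Entry | 4.1, 4.2 | Bleeding restriction applies only to HIV-positive applicants |
| Kits at entry | 5.4.2 | HemaSpot goes to HIV-positive participants |
| Reported positive result | 5.4.3 | Care Navigator contact, linkage to care, help with confirmatory testing |
| Access to kits after seroconversion | 8.2 | Confirmatory testing is the only stated condition |
| Mailing | 5.2 | Address confirmed, participant aware a package is coming |
| Risks and discontinuation | 8.3, 8.4, 11.2.1 | Bleeding named as a finger-prick effect in 11.2.1; no check linked to hemophilia or anticoagulants |

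An HIV-negative or status-unknown person with hemophilia passes 4.1 and 4.2. If that person later has a confirmed positive test, 8.2 makes them eligible for the kit. None of the steps between is described as asking about bleeding risk.

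**Scale**

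Inputs from the documents:
- Randomised HIV-negative or status-unknown participants: 2 arms × 150 = 300 (3.2; 5.1 gives the same total).
- Referred peers: about 300 (4.1, 5.1), of whom half are estimated to be HIV-negative or status-unknown (3.2), so 150.
- N = 300 + 150 = 450. The range is 300 if no such peers enrol, to 600 if all peers are of this kind.

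Inputs that are assumptions, because the documents give no rates:
- s, the share who become HIV-positive in the study: 0.01 to 0.05.
- b, the share with hemophilia or current anticoagulant use: 0.001 to 0.01.

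Expected number affected = N × s × b:
- N = 450, low: 450 × 0.01 × 0.001 = 0.0045
- N = 450, high: 450 × 0.05 × 0.01 = 0.225
- N = 300, low: 300 × 0.01 × 0.001 = 0.003
- N = 600, high: 600 × 0.05 × 0.01 = 0.30

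Probability of at least one such person = 1 − (1 − s × b)^N:
- N = 450: 1 − (1 − 0.00001)^450 = 0.0045, to 1 − (1 − 0.0005)^450 = 0.2015
- N = 300, low: 1 − (1 − 0.00001)^300 = 0.003
- N = 600, high: 1 − (1 − 0.0005)^600 = 0.259

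A seroconverter joins after the baseline kit, so at most two scheduled kits remain (months 6 and 12). Expected scheduled kits are then at most 2 × 0.225 = 0.45 for N = 450, and 2 × 0.30 = 0.60 for N = 600.

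**Effect on the analysis**

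Section 10.2 defines the primary outcome by HIV status at baseline. A seroconverter stays in the HIV-negative/unknown stratum, where the outcome is repeat testing. Withholding a kit from that person removes no viral load from the HIV-positive primary comparison.

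**The case against.** The strongest objection is that the point is immaterial. Under any of the assumptions above the expected number is below one, and the protocol rates the finger prick as no more than minimal risk. That supports a low priority. It does not remove the inconsistency, since the same protocol still restricts HIV-positive applicants on this ground.

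The rates are also assumed, and s may not describe the right group: status-unknown entrants who were already infected and upload a positive test reach the same rule. This is fair. The expected number is proportional to s, so doubling s would double it.

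There are safeguards before a kit goes out. A seroconverter has confirmatory testing, and section 5.4.3 says "our Care Navigator will reach out within 3 business days to support and facilitate linkage to resources and care". Section 5.2 adds: "Study staff will not send mail unless the participant has confirmed their mailing address and is aware they will be receiving a package". Section 8.2 confers eligibility and obliges no one to use a kit, and 8.4 lets the principal investigator withdraw a participant in that person's interest. These are real opportunities to catch a problem, but none is described as asking about bleeding, and discretion under 8.4 helps only if the condition is known.

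The screener, surveys, instructional booklet, operating procedures and consent form are not in the documents, and any of them might contain the question. This stands as a limit: the conclusion is about the protocol text. Since the entry restriction is in the protocol, its continuation belongs there too.

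Finally, an HIV-positive participant who starts an anticoagulant after baseline would also receive later kits with no described re-check. That is correct. It is a second gap of the same kind and does not answer the first.

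**Conclusion.** The concern holds. The protocol restricts a procedure for people with bleeding risk at entry and then opens the same procedure to seroconverters without that restriction. It is a small participant-safety inconsistency, worth considering but not urgent. On the assumed rates, 0.0045 to 0.225 people would be affected at N = 450 (0.003 to 0.30 across N = 300 to 600), and the chance of at least one is about 0.5% to 20% (0.3% to 26%). Confidence is high about the wording. Whether a gap exists in practice depends on documents not available here, and the purpose of the entry restriction is inferred. The primary analysis and power are unaffected.

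**What to change.** Add a sentence to 8.2, repeated in 5.4.2: before a seroconverter's first HemaSpot kit is sent, staff ask the hemophilia/anticoagulant question from 4.1, and the kit is withheld if the answer is yes. The Care Navigator contact (5.4.3) or the address confirmation (5.2) is a natural moment to ask it. Asking the same question before every kit would also cover HIV-positive participants who start an anticoagulant later, if the sponsor wants the restriction to follow the procedure throughout.

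For seroconverters the cost is one sentence in two places and one question each. At most a few viral loads would be missing, none of them from the HIV-positive primary analysis.

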8.3 Intervening on "Social Harms"

Potential Risks

We identified the following items as possible risks to subjects and described how we plan on addressing those risks:

- 1. Emotional discomfort: Some participants may be uncomfortable answering questions about their past and/or current HIV risk behaviors (e.g., sexual behavior, substance use). Participants may also feel uncomfortable answering questions about their sexual attractions, or their sexual and gender identity. However, it is important to note that emotional discomfort is an event encountered routinely in daily life and potential discomfort would likely not exceed what is typically encountered in these youths' experiences. All information used in enrollment and recruitment describing the research activities will include a detailed description of the content and expected participation of the respondent, such that the respondent is aware of the nature of the questions to be included in the surveys. The study app will provide these details in full, during the consent process, and once the participant has created their password protected profile they will be able to access full information on the expectations of participation and the types of questions they will be asked. Informed consent documents will inform research participants of the need to keep answers to questions confidential.
- 2. **Psychological distress** is a potential risk to participants during the completion of the surveys, reading the intervention content and during the qualitative interviewing. We will provide participants with information to allow them to contact the study team at any time if they experience psychological distress related to participation in the study. If psychological distress is apparent, we will refer crisis cases to the National Runaway Safeline which is available 24 hours a day, 7 days a week. We will use established protocols from our prior studies conducted with youth and men who have sex with men (MSM) for research staff to guide them in responding to crisis or harm situations, including attempting to contact the participant to assess risk level and provide appropriate follow-up (e.g., crisis hotline, safety check, suicide hotline). We will notify participants when we must engage in mandatory reporting during the consent process and when the participant decides to share a reportable event with study staff.
- 3. **Unintended disclosure** is also a potential risk. Data will be protected by extensive confidentiality procedures as described below. Data will be collected confidentially; this will be fully described in the informed consent. We have extensive data procedures already in place to ensure security of the data and information provided by participants:

- Data will be encrypted at all times, from the point of entry into CASI to the point of backup and to analysis. Data will be encrypted using standardized software (e.g., 256-bit, PGP).
- Data will be de-identified and linked by the Study ID to minimize risk of inadvertent disclosure.
- Data will not be released to non-study staff at any time.
- All electronic data sharing between sites will be done only on the secure server.

Study staff will be trained on confidentiality standards and proper interviewing techniques. This will include the following points:

- Always maintain anonymity of the participant data and confidentiality of person.
- Participant names will not be included in any data collection instruments, biomarker containers, or intervention forum posts. The only numbers used to label and identify data from the participant are the Participant ID or their username (app handle) for the intervention.
- Questionnaires and audiotapes are to be linked using the Survey ID number and the interview date. No personal identifiers should be written or affixed to the test results or lab slips.
- Protect the electronic security of all databases.
- Computers that can access electronic data should be physically secured and should be protected by coded passwords. Networks must be demonstrated to be secure by the IT department prior to use.
- Only authorized persons are to have access to electronic databases.
- Project staff must shred documents containing sensitive information before disposing of them.
- 4. Privacy and confidentiality concerns: Participants will be reminded at the beginning of each survey to consider their surroundings and the privacy of their device and internet connection. All communication between study staff and participation will not include sensitive information about HIV, MSM, or anything that may reveal their participation in a study or answers to any of the questions answered in the surveys.

Participants will be asked to provide two forms of contact information. Because participants are providing these pieces of identifiable information, there is a possibility that their participation in a research study could be disclosed in the following ways: (1) if someone other than the participant sees the intervention content; (2) if someone besides the participant reads the email sent with the link to the follow-up survey in which participants will enter their results; or (3) if someone besides the participant sees the study text messages, or online surveys on participants' computer, tablet or phone. The risk of disclosure of participation in a research study through receiving study related emails, receiving text messages, interacting with the online surveys or with the study application on the participants' cell phone will be minimized in the following ways: (1) participants must enter a PIN to gain access to the app if it has been 5 minutes since the app was open on their device, or 15 minutes if the app was open but inactive as a fail-safe to avoid unintended disclosure; (2) emails with a links surveys will not make any reference to the nature of the survey; (3) participants will be encouraged to delete any text messages received as part of the study to protect them from an unauthorized individual viewing the messages, and to interact with the study application when in private (e.g., turn on screen lock, complete surveys when alone). Participants will be notified of these risks in the consent process.

- 5. Emotional distress: Participants who learn that they are HIV-positive during the course of the study may be distressed to learn of their health condition. This poses the greatest emotional and physical risk to participants in the research study. The informed consent documents will outline the HIV testing process, stating that results will be delivered the same day for HIV testing, and will explain in full what a positive, negative, or indeterminate HIV test result means. Individuals who receive a positive HIV test result will be offered counseling, confirmatory testing, and referrals to care that are appropriate to their economic situation (e.g. those eligible for Ryan White Care will be linked to the appropriate services). All those receiving a positive result will be linked directly to the Care Navigator who can assist them in finding appropriate resources and/or linking to a case manager at a local agency.
- 6. **Risk of coercion**: Although most participants in our trial will be recruited using online advertisements, participants in the HMP open network intervention arm (Peer-referral network, Intervention Arm 2) will be incentivized to refer two eligible peers into the study. Our consent processes and instructions for peer referral will ask participants to avoid unintentionally coercing peers. Peers who are invited into the study will have access to consent documents which will fully explain the study procedures, potential risks, and potential benefits. Referred peers will also be reminded that the study participation is voluntary and that refusing to participate in the study or withdrawing from the study is an option at any time.
- 7. Risk of offensive/upsetting language or cyber bullying: We will strive to create a safe and comfortable app environment for all study participants. However, it is possible that participants in the two treatment arms may experience emotional discomfort or upset due to things other participants post through the intervention app' forums. The forums are monitored by study staff, however we do not require posts to be pre-approved by study staff before they go live in the app. We will include "community guidelines" as part of the intervention app's on-boarding process. This information is also included within the app as its own screen and reminders will be provided at all study follow-up assessments. These guidelines were developed and used successfully for participants in the original HMP intervention. Indeed, only one post out of 1497 posts met the criteria for a guideline violation. Thus, we believe the likelihood and seriousness of this risk is minimal. During the adaptation and final development of HMP Stigma we will ask Youth Advisory Board members to review and help update the guidelines to ensure they are comprehensive given the regular evolution of online environments and social media tools. The guidelines will continue to include language around non-discrimination, non-offensive language, openness and confidentiality. As in the original HMP intervention, during the study RCT, study staff will monitor all participant posts during business hours with posts made outside of business hours reviewed in the morning of the next business day. If a participant posts something that could be considered in breach of the guidelines, study staff will remove the post, contact the participant to notify them, explain why the post was removed, provide them with a copy of the guidelines to review again and post a note from the study team to the forum reminding all participants to review and adhere to the guidelines. If a participant accumulates three violations of this nature, they will be immediately discontinued from the study. Any threat of harm to others would be grounds for considering immediate study

stop. The reason we choose to allow more than one violation is that one of the key mechanisms of change for the intervention is for participants to become more aware of the conscious and unconscious stigmatizing beliefs they hold – as well as to challenge these stigmatizing views in others. Thus, we think that these violations can provide a learning opportunity for all parties if handled intentionally. The grounds for discontinuation will be made clear during the informed consent process and will be stated explicitly online within the app use guidelines. Study protocol will include a Standard Operating Procedures manual for staff that will include directions for referral and follow-up in the event that a participant expresses emotional discomfort, distress, threats to self or others, or suicidality.

